#### **5.4.1.2. Slow Vital Capacity Percent Predicted**

##### **5.4.1.2.1. Estimand**

The 5 attributes for the estimand related to SVC percent predicted are described as follows:

- Treatment: ravulizumab or placebo with or without the use of stable riluzole and edaravonee
- Population: adult participants with ALS as defined by the protocol inclusion/exclusion criteria and included in the FAS
- Variable: change from Baseline in SVC percent predicted at Week 50 based on the in-clinic assessment or the at-home assessment when in-clinic assessment is not available
- ICE: none. The treatment-policy strategy will be adopted.
- Population-level summary: mean change from Baseline in SVC percent predicted at Week 50; the treatment effect will be quantified by the difference in mean between ravulizumab and the placebo arms.

##### **5.4.1.2.2. Main Analytical Approach**

The treatment effect on SVC percent predicted will be evaluated based on a mixed-effect model repeated measure with the change from Baseline in SVC percent predicted as the dependent variable and the following list of independent variables as fixed effects: actual time on study (months), time and treatment interaction, age, sex, baseline ALSFRS-R total score, baseline SVC, disease duration, and the stratification factor. In addition, the participant-specific random slope will be added to the model with an unstructured variance-covariance matrix. The strategy for selecting other covariance structures outlined in Section 5.3.3.1.2 will be used if a convergence issue occurs. The Kenward-Rogers method will be used to estimate the denominator degrees of freedom. No imputation for the missing data will be performed after death or discontinuation, assuming the data are MAR.

A 2-sided p-value less than  $\alpha = 0.05$  associated with the higher mean change in SVC percent predicted in the ravulizumab group compared to placebo will indicate a statistically significant treatment benefit. The LS-means and the 95% CIs of the mean change from Baseline at Week 50

(month 11.5) for each treatment arm and the difference between the arms will be calculated. Details will be provided in a listing.

#### **5.4.1.3. Other Analyses for Slow Vital Capacity**

The absolute values and changes from Baseline will be summarized by visits for the SVC data. Figures of the mean values and the changes from Baseline over time will be provided, along with 95% CIs. Details will be provided in listings.

#### **5.4.2. Supportive Secondary Endpoints and Analysis**

##### **5.4.2.1. Muscle Strength Measured by Handheld Dynamometry**

The absolute values and changes from Baseline will be summarized by visits for the HHD data. Figures of the mean values and the changes from Baseline over time will be provided along with 95% CIs. Details will be provided in listings. See Section 6.2.6 for additional details.

##### **5.4.2.2. Neurofilament Light Chain (NfL) Concentration**

The absolute values and the log-transformed values will be summarized by visits. Figures of the geometric means over time will be provided along with 95% CIs. Details will be provided in listings.

#### **5.5. Tertiary/Exploratory Endpoints and Analyses**

No analyses and no any summary tables or listings will be done for any tertiary/exploratory endpoints.

#### **5.6. Safety Analyses**

The safety analyses will be descriptive in nature and will include the following:

- Exposure to IP
- AEs
- Laboratory data
- Vital signs
- ECG
- Physical examination
- Neurological examination
- C-SSRS
- Exposure to COVID-19

All safety analyses for the RCP and OLE Period will be conducted based on the Safety Set (SS) and OLE Set.

##### **5.6.1. Extent of Exposure**

Descriptive statistics will be generated for the variables described in [Table 4](#).

**Table 4: Variables for Study Duration, Exposure, and Treatment Compliance**

Variable (Unit)	Study Period (Population)	Definition	Calculation
Duration			
Duration of RCP participation (days)	RCP (SS)	Number of days from informed consent to last day in RCP.  Note: The last day in RCP is defined as the latest of RCP completion, discontinuation date, date of death, or date of the follow-up visit from RCP.	Date of last day in RCP -date of informed consent + 1
Duration of study participation (days)	RCP and Study (SS)	Number of days from informed consent to last day in study.  Note: The last day in the study is defined as the latest of study completion or discontinuation date or date of death or date of the follow-up visit from the study	Date of last day in the study - date of informed consent + 1
Treatment duration (days) - RCP	RCP (SS)	Number of days on study treatment from first study drug infusion until the last study drug infusion during RCP.  Note: Week 50 dosing will not be included in this calculation.	Last study drug infusion date in RCP - first RCP study drug infusion date + 1
Treatment duration (days) – OLE	OLE (OLES)	Number of days on study treatment from first OLE study drug infusion until the last study drug infusion during OLE.	Last study drug infusion date in OLE - first OLE study drug infusion date + 1
Duration of RCP (days)	RCP (SS)	Number of days from first study drug infusion to last day in RCP.	Date of last day in RCP - date of the first infusion in RCP + 1
Total patient-years (years) – RCP	RCP (SS)	Total RCP duration (years) for all participants.	Sum of RCP duration (days) / 365.25 for all participants
Duration of OLE (days)	OLE (OLES)	Number of days from first OLE study drug infusion to last day in OLE.	Date of last day in OLE - date of the first infusion in OLE + 1
Total patient-years (years) – OLE	OLE (OLES)	Total OLE duration (years) for all participants.	Sum of OLE duration (days) / 365.25 for all participants
Exposure			
Total number of infusions	RCP (SS)	Total number of infusions in RCP  Note: Infusions with an interruption at the same visit will be counted once.	The total number of infusions in RCP.
Total number of loading dose infusions	RCP (SS)	Total number of loading dose infusions	The total number of loading dose infusions in RCP.
Total number of maintenance dose infusions	RCP (SS)	Total number of maintenance dose infusions	The total number of maintenance dose infusions in RCP.
Total dose administered (mg)	RCP (SS)	Total dose administered	Sum of all doses in RCP. Note: Placebo kits will contribute to zero doses.
	OLE (OLES)	Total dose administered	Sum of all doses in OLE. Note: Placebo kits will contribute to zero doses.
Total infusion volume (mL)	RCP (SS)	Total infusion volume	Sum of all infusion volume in RCP.
	OLE (OLES)	Total infusion volume	Sum of all infusion volume in OLE.

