**Table 1: Randomization Strata**

Strata	ALS Muscle Weakness at the Onset	Background ALS Therapy (Riluzole or Edaravone) at Study Entry	
	(Bulbar vs. Not)	On Stable Riluzole	On Stable Edaravone
1	Not bulbar	No	Yes, No
2	Not bulbar	Yes	Yes
3	Not bulbar	Yes	No
4	Bulbar	No	Yes, No
5	Bulbar	Yes	Yes
6	Bulbar	Yes	No

a Stable riluzole: at least 30 days on riluzole prior to Day 1.

b Stable edaravone: at least 60 days on edaravone prior to Day 1.

Abbreviations: ALS = amyotrophic lateral sclerosis; vs = versus

Patients who do not enter the study on riluzole and/or edaravone will not be permitted to start treatment with either drug during the RCP.

[figure not shown]
One unblinded interim analysis for futility is planned when approximately 33% of originally planned patients (N = 354) complete the Week 26 visit for the RCP. An independent data monitoring committee (IDMC) will be established to conduct this unblinded interim analysis and periodic review of accumulating data for patient safety and efficacy during the study. Details of the interim analysis methods are described in a separate interim analysis plan (IAP).

**OLE Period:** For each participant, the RCP ends, and the OLE Period starts, when the participant has completed the Week 50 visit assessments and received the first dose for the OLE. Regardless of the randomized assignment, all patients will receive ravulizumab during the OLE Period. Blind to the randomized treatment assignment will be maintained for patients and providers during the OLE Period until the end of the study. Initiation of riluzole and/or edaravone is permitted during the OLE Period. The first dose of the OLE Period will be administered in a blinded fashion to accommodate the loading dose for the patients originally randomized to placebo (see protocol for further details).

The OLE Period will continue for up to 2 years or until ravulizumab is approved and/or available (per country-specific regulations), whichever occurs first.

After the End of Treatment Visit or early discontinuation, patients will be followed for an additional 8 weeks after their last dose of the study drug.

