**Table 5: Definition of TEAEs**

TEAE (RCP)	TEAE (OLE)
For RCP participants entering the OLE, a TEAE will be defined as any AE with onset on or after the first dose of IP in the RCP up to and including the day prior to the first OLE dose.	A TEAE will be defined as any AE with onset on or after first dose of OLE.
For RCP participants not entering the OLE, TEAE will be defined as an AE with onset on or after the first RCP dose of IP.	

If the time of the AE onset is available, it will be used to determine the treatment emergence by comparing with the time of the first study drug infusion, ie, if the AE onset time is prior to the time of infusion, it will not be considered as treatment-emergent.

Abbreviations: AE = adverse event; IP = investigational product; OLE = Open-Label Extension; RCP = Randomized Controlled Period; TEAE = treatment-emergent adverse event

The incidence, toxicity, and relationship to IP will be summarized by the treatment group. Specific AEs will be counted once for each participant for calculating percentages (e.g., overall, SOC, PT). In addition, if the same AE occurs multiple times for a participant, the highest severity and relationship to IP observed will be reported. All TEAEs will be summarized overall and categorized by MedDRA SOC and PT. The ordering of SOC will be alphabetical, and the ordering for PT will be most prevalent (using percentage) PT within each SOC based on the ravulizumab (RCP analysis) or total column (OLE). PTs with the same number of participants (eg, to break ties) will be further sorted by the number of events and then alphabetically.

Table 6 provides an overview of the tabular summaries of AEs for different periods, underlying analysis sets, and treatment group display convention. An “X” in the table represents that an analysis will be performed for the period. For incidence tables, the number of participants and percentage will be tabulated; percentages will be based on the number of participants in the respective treatment groups. For event-rate tables, the rate per 100 patient-years will be calculated as follows (see Table 4 for the definition of patient-years):

$$= 100 \times \frac{\text{Total number of TEAEs for specific reporting period}}{\text{Total Person years for specific reporting period}}$$

The following participant-level listings will be generated for AE data:

- All AEs
- All SAEs
- AEs leading to study drug discontinuation
- AEs leading to death
- AEs of special interest

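### SAP Table 4 does not confine the last day in the RCP to the RCP, so RCP patient-years can take in open-label time that the RCP adverse-event count excludes

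*SAP*

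**What the plan says.** The note in SAP Table 4 (Section 5.6.1) reads "The last day in RCP is defined as the latest of RCP completion, discontinuation date, date of death". The fourth date in its list is the RCP follow-up visit. Only the completion date and the follow-up visit carry the word RCP.

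Three quantities depend on that day:

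- RCP duration: "Date of last day in RCP - date of the first infusion in RCP + 1".
- RCP patient-years: "Sum of RCP duration (days) / 365.25 for all participants".
- Duration of RCP participation, counted from informed consent to the same last day.

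Section 5.6.2 carries the patient-years into the event rates: "the rate per 100 patient-years will be calculated as follows (see Table 4 for the definition of patient-years"). The numerator is bounded. For participants who enter the OLE, Table 5 counts events by this rule: "onset on or after the first dose of IP in the RCP up to and including the day prior to the first OLE dose".

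Section 1.2 also bounds the period itself: a participant's RCP closes, and the OLE opens, once the Week 50 assessments are done and the first OLE dose has been given. Table 4 starts OLE duration at the first OLE infusion.

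**The concern.** The numerator and denominator of the RCP event rate are closed by different rules. For an OLE entrant the event count stops the day before the first OLE dose. The person-time runs to the latest of four dates, and a death date in the OLE meets the wording of the note. The absorbed days bring no RCP events with them, so the error can only lower the RCP rate. The same days also enter OLE patient-years, so they are counted twice.

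Everyone in the OLE receives ravulizumab, so under the literal rule the placebo arm's RCP patient-years would include time on active drug. What is at stake is the patient-year-adjusted rates, which Protocol Section 9.4.6.1 says will be produced, and the RCP duration and patient-years summaries that Table 4 lists for reporting.

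**Working it through.** The documents give no patient-years total and no event rate, so there is no stated figure to reproduce. The check applies the Table 4 formula directly.

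**Inputs from the documents.** Week 50 is Day 351 (SAP Table 23). RCP TEAEs for an OLE entrant end the day before the first OLE dose (Table 5), which is Day 350 if that dose is given on Day 351. The OLE lasts up to 106 weeks (Protocol Section 8.1.4).

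**Assumptions.** *w* is the number of weeks from the first OLE dose to a later death or discontinuation date. *f* is the share of the Safety Set with such a date. *m* is the mean RCP duration in days of everyone else. None of these is in the documents.

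**One participant.** Literal RCP days = 351 + 7*w*. Days matching the numerator = 350, or 350/365.25 = 0.958 patient-years.

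| *w* (weeks) | Literal days | Patient-years | Factor (literal/350) |
|---|---|---|---|
| 8 | 407 | 1.114 | 1.16 |
| 26 | 533 | 1.459 | 1.52 |
| 52 | 715 | 1.958 | 2.04 |
| 106 | 1093 | 2.992 | 3.12 |

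**Whole group.** Matched mean = (1 − *f*)*m* + 350*f*. Literal mean = (1 − *f*)*m* + *f*(351 + 7*w*). The rate is understated by 1 − matched/literal. With *w* = 26 and *m* = 280:

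- *f* = 2%: matched 274.4 + 7.0 = 281.4; literal 274.4 + 10.66 = 285.06; understated by 1.3%.
- *f* = 5%: matched 266 + 17.5 = 283.5; literal 266 + 26.65 = 292.65; understated by 3.1%.
- *f* = 10%: matched 252 + 35 = 287; literal 252 + 53.3 = 305.3; understated by 6.0%.
- *f* = 25%: matched 210 + 87.5 = 297.5; literal 210 + 133.25 = 343.25; understated by 13.3%.

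Over *f* from 1% to 50%, *w* from 8 to 52 weeks and *m* from 200 to 351 days, the understatement runs from about 0.2% to about 40%. The width of that range shows how little the documents fix the size; it is not an estimate.

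**One-day overlap.** An OLE entrant with no later date, whose RCP completion and first OLE dose both fall on Day 351, still has 351 days of RCP time against a numerator ending on Day 350. That is 1/351, about 0.3% of that participant's RCP time.

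**Participants who do not enter the OLE.** Table 5 puts no upper limit on their TEAEs, and their RCP time runs through follow-up, so the mismatch does not arise.

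**The case against.** The strongest reply is that the intent is plain. Section 1.2 ends the RCP at the first OLE dose, so a later date cannot be a day in the RCP. Table 5 stops RCP events just before that dose, and Table 23 closes the Week 50 window on the day of it. Table 4 has a separate row for study participation with its own last day in the study; if OLE dates counted as RCP dates, the two rows would coincide for those participants. The list opens and closes with the word RCP, and Section 5.2 reports discontinuation reasons separately for RCP and OLE. The natural reading of the discontinuation date is therefore discontinuation from the RCP.

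Most of this stands. It shows what was meant, and a careful programmer may apply the boundary unprompted. It does not dispose of the death date, which has no period attached and sits under an instruction to take the latest date.

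A reader might infer more: that because the study was stopped for futility, everyone then in the OLE has a discontinuation date there, so the effect must be large. The documents do not support that. It requires rejecting the natural reading of the discontinuation date, and no count of OLE participants or of their time in the OLE is given. The SAP's list of changes (Section 6.4) describes the OLE data as small in amount. A reader might also infer a biased comparison between arms; that follows only if the proportion of absorbed time differs by arm, and nothing in the documents shows that it does.

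**Conclusion.** This is a minor but real specification error. Table 4's rule for closing RCP time, taken as written, conflicts with the RCP boundary used elsewhere in the SAP and gives a wrong denominator for anyone who dies after entering the OLE. For OLE discontinuations the wording is ambiguous rather than wrong.

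The direction is certain if the rule is applied literally: RCP rates per 100 patient-years too low, RCP durations too long. The size is not known. The illustrative figures of 1.3% to 13.3% rest on an assumed OLE date at 26 weeks, an assumed mean of 280 RCP days for the others, and affected shares of 2% to 25%. Given the SAP's description of the OLE data, and more so if only deaths qualify, the low end is the more plausible. Safety analyses are descriptive, and incidence counts and percentages do not use patient-years. The text shows that the rates can be diluted, not that they will be.

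**What to change.** Replace the note in Table 4 with: *For participants treated in the OLE, the last day in RCP is the day before the first OLE dose. For all others, it is the latest of RCP completion, RCP discontinuation, death, or the RCP follow-up visit.*

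The first sentence aligns person-time with the TEAE cut-off in Table 5 and removes both the double counting and the one-day overlap. RCP completion must stay in the second sentence: Section 5.2 recognises participants who do not roll over into the OLE, and someone who completes the RCP without rolling over has no RCP discontinuation date.

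The cost is an amended table note and one date derivation in the programs. It needs no new data, and the SAP amendment is due to be finalized before the final database lock.

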**Table 4: Variables for Study Duration, Exposure, and Treatment Compliance**

Variable (Unit)	Study Period (Population)	Definition	Calculation
Treatment Compliance			
Number of participants with an infusion interruption for any reason	RCP (SS)	Number of participants with an infusion interruption at any time (for any reason) during loading dose or maintenance dose infusion in RCP.	Count of participants with an infusion interruption (for any reason) at any time during loading dose or maintenance dose infusion in RCP.
Number of interrupted infusions for any reason per participant	RCP (SS)	Total number of interrupted infusions (for any reason) per participant at any time during loading dose or maintenance dose infusion in RCP.	Sum of all instances of infusion interruption (for any reason) in RCP.
Number of participants with an infusion interruption for AEs	RCP (SS)	Number of participants with an infusion interruption at any time (for AEs) during loading dose or maintenance dose infusion in RCP.	Count of participants with an infusion interruption (for AEs) at any time during loading dose or maintenance dose infusion in RCP.
Number of interrupted infusions for AEs per participant	RCP (SS)	Total number of interrupted infusions (for AEs) per participant at any time during loading dose or maintenance dose infusion in RCP.	Sum of all instances of infusion interruption (for AEs) in RCP.
Percent compliance	RCP (SS)	Percentage of the total number of infusions administered out of the total number of expected infusions during RCP.	$100 \times (\text{Total number of infusions administered in RCP}) / (\text{Total number of expected infusions in RCP})$
Percent compliance category	RCP (SS)	Percent compliance categories range from 100% to 0% by decrements of 10% per category.	100%, 90% to < 100%, 80% to < 90%, etc.

Abbreviations: AE = adverse event; OLE = Open-Label Extension; OLES = Open-Label Extension Set; RCP = Randomized Controlled Period; SS = Safety Set

### 5.6.2. Adverse Events

AEs will be coded to the corresponding system organ class (SOC) and preferred term (PT) using the latest available version of the MedDRA.

The definitions of TEAE provided in [Table 5](#) will be used to analyze AEs for different study periods. The TEAE (RCP) and TEAE (OLE) represent TEAEs during RCP and OLE, respectively. For handling missing dates of onset, refer to [Section 6.2.1](#). AEs with onset prior to the first administration of study drug will be summarized as pretreatment AEs.

**Table 5: Definition of TEAEs**

TEAE (RCP)	TEAE (OLE)
For RCP participants entering the OLE, a TEAE will be defined as any AE with onset on or after the first dose of IP in the RCP up to and including the day prior to the first OLE dose.	A TEAE will be defined as any AE with onset on or after first dose of OLE.
For RCP participants not entering the OLE, TEAE will be defined as an AE with onset on or after the first RCP dose of IP.	

If the time of the AE onset is available, it will be used to determine the treatment emergence by comparing with the time of the first study drug infusion, ie, if the AE onset time is prior to the time of infusion, it will not be considered as treatment-emergent.

Abbreviations: AE = adverse event; IP = investigational product; OLE = Open-Label Extension; RCP = Randomized Controlled Period; TEAE = treatment-emergent adverse event

The incidence, toxicity, and relationship to IP will be summarized by the treatment group. Specific AEs will be counted once for each participant for calculating percentages (e.g., overall, SOC, PT). In addition, if the same AE occurs multiple times for a participant, the highest severity and relationship to IP observed will be reported. All TEAEs will be summarized overall and categorized by MedDRA SOC and PT. The ordering of SOC will be alphabetical, and the ordering for PT will be most prevalent (using percentage) PT within each SOC based on the ravulizumab (RCP analysis) or total column (OLE). PTs with the same number of participants (eg, to break ties) will be further sorted by the number of events and then alphabetically.

Table 6 provides an overview of the tabular summaries of AEs for different periods, underlying analysis sets, and treatment group display convention. An “X” in the table represents that an analysis will be performed for the period. For incidence tables, the number of participants and percentage will be tabulated; percentages will be based on the number of participants in the respective treatment groups. For event-rate tables, the rate per 100 patient-years will be calculated as follows (see Table 4 for the definition of patient-years):

$$= 100 \times \frac{\text{Total number of TEAEs for specific reporting period}}{\text{Total Person years for specific reporting period}}$$

The following participant-level listings will be generated for AE data:

- All AEs
- All SAEs
- AEs leading to study drug discontinuation
- AEs leading to death
- AEs of special interest
- Infusion reaction related AEs
- COVID-19 AEs

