##### **9.4.6.1. Analysis of Adverse Events**

Analysis and reporting for AEs will be based on treatment-emergent AEs, including treatment-emergent SAEs (TESAEs) defined as an AE with onset on or after first dose of study drug administration in the Randomized Controlled Period. Treatment-emergent AEs and TESAEs will be summarized by MedDRA SOC and Preferred Term and by relationship to the study drug; TEAEs will also be summarized by severity. Patient-years adjusted event rates will be generated to characterize long-term safety profile.

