**Table 23: Analysis Windows for Randomized Controlled Period**

Analysis Visit	Target Day	Low	High
Week 2	15	2	29
Week 6	43	30	57
Week 10	71	58	85
Week 14	99	86	113
Week 18	127	114	141
Week 22	155	142	169
Week 26	183	170	211
Week 34	239	212	267
Week 42	295	268	323
Week 50	351	324	For participants entering OLE, the day of first dose in OLE; the last day in the study for other participants

The analysis visits for the OLE Period will be derived using prespecified windows around the number of days during the study since the first dose of the OLE Period. The lower and the upper limits of the analysis windows are described in [Table 24](#).

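### An adverse event that starts on the Week 50 switch day before the first extension infusion can never be a randomised-period TEAE, and SAP Table 5 leaves open whether it counts in either period

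*SAP*

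**What the plan says.** SAP 5.6.2, Table 5, defines TEAEs separately for the two periods.

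- **RCP, participants entering the OLE:** onset from the first RCP dose "up to and including the day prior to the first OLE dose".
- **OLE:** "A TEAE will be defined as any AE with onset on or after first dose of OLE".
- **Note under the table:** "If the time of the AE onset is available, it will be used to determine the treatment emergence", by comparison with the first study drug infusion; "if the AE onset time is prior to the time of infusion, it will not be considered as treatment-emergent". The note does not name a period.

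The text above Table 5 adds a pretreatment class: "AEs with onset prior to the first administration of study drug will be summarized as pretreatment AEs".

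Two other places set the boundary differently. SAP 1.2 ends the RCP and starts the OLE "when the participant has completed the Week 50 visit assessments and received the first dose for the OLE". Protocol 9.4.6.1 has no upper limit: a TEAE is "defined as an AE with onset on or after first dose of study drug administration in the Randomized Controlled Period".

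The Week 50 dose is the first OLE dose, and it is given blinded (Protocol 6.3.2 and 8.1.4.2).

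**The concern.** The RCP window closes by calendar date, while the note can close the OLE window by clock time. The hours of the switch day before the infusion are therefore outside the RCP window, and they may be outside the OLE window too. A participant in those hours has had only randomised treatment.

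At stake is which treatment an event is reported under. An event in a placebo participant who has not yet received ravulizumab could appear under Placebo/Ravulizumab in the OLE tables, or in no TEAE table at all. The study stopped for futility and SAP 5.1 makes all p-values descriptive, so the safety comparison is one of the main remaining outputs. Two programmers following Table 5 could classify the same event differently.

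**Working it through.** The plan gives no figure to reproduce, and the documents give no count of switch-day events. The check is one of logic.

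**1. Is there a pre-infusion interval on the switch day?** Yes. Protocol 8.1.4 places the infusion after all other tests and procedures at a dosing visit, apart from post-dose samples. Protocol 8.1.4.2 has the participant complete the Week 50 predose assessments before receiving ravulizumab.

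**2. Does any other rule pick up an event in that interval?** No. The pretreatment class covers only events before the first administration of study drug. The partial-date rules in SAP 6.2.1 refer to the first or last study drug administration and do not address the switch day.

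**3. Apply the rules to test cases.** Assume, for illustration, a first OLE infusion at 10:00 on Day 351. Reading A applies the note to the first infusion of each period. Reading B applies the note to Day 1 only and treats the OLE start as a date. The last column uses the rule proposed below, with untimed events going to the OLE.

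| Onset | RCP TEAE (A or B) | OLE TEAE, reading A | OLE TEAE, reading B | Proposed rule |
|---|---|---|---|---|
| Day 350 | yes | no | no | RCP |
| Day 351, 08:00 | no | **no** | yes | RCP |
| Day 351, no time | no | yes | yes | OLE |
| Day 351, 12:00 | no | yes | yes | OLE |
| Day 352 | no | yes | yes | OLE |

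Under both readings no Day 351 event can be an RCP TEAE. Under A, the timed 08:00 event is in neither period. Under B, it is charged to the OLE. Under the proposed rule, each case falls in exactly one period.

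**4. What does assignment to the OLE change?** SAP Table 6 marks only its first six TEAE summaries for the OLE. The summaries by severity, by relationship to study drug, for the AE of special interest (meningococcal infection) and for infusion reactions are marked for the RCP only. An event moved to the OLE leaves all of them.

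**5. How large is the interval?** One day in 351 is 1/351 = 0.28% of RCP days for a participant who reaches Day 351. That is a ceiling on time, because only the hours before the infusion are affected. It does not estimate the share of events.

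**The case against.** A reader might infer more: that every switch-day event before the infusion is in neither period, drops out of every TEAE table and is lost from the safety record. The documents do not support that, for four reasons.

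- **Untimed events.** The note operates only when an onset time is available. Without one, the event is assigned by date to the OLE. It is misattributed but still tabulated. The documents do not say how often a time is recorded.
- **Which infusion the note means.** SAP 6.1.1.1 and 6.2.9 equate the first infusion or first dose of study drug, with no period named, with Day 1. SAP Table 4 names the OLE explicitly when it means the OLE infusion. On that usage the note concerns Day 1 only and, with a date-level OLE start, nothing is lost. This reading is at least as natural as the other.
- **Listings.** The listings in SAP 5.6.2 cover all AEs and all SAEs, not only TEAEs. A serious event could miss a summary table but would still be listed.
- **Few participants.** SAP Appendix 4 describes a small amount of OLE data, and safety analyses are descriptive.

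Nor is it decisive that SAP Table 23 extends the RCP Week 50 window to include, "For participants entering OLE, the day of first dose in OLE". That window maps visit assessments, which are done before the infusion, so it need not match an AE window.

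The protocol also places the boundary slightly earlier than SAP 1.2 does. Protocol 3.1 ends the RCP when the Week 50 assessments are complete, without waiting for the dose. This matters only for an event between the last assessment and the infusion. Earlier hours of that day are in the RCP under both documents, and Table 5 excludes them.

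These points limit the size of the problem. None of them lets a switch-day event count as an RCP TEAE.

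**Conclusion.** The point holds in this form: Table 5 is wrong as written, with low severity. It excludes from the RCP an interval that SAP 1.2 places in the RCP and that Protocol 9.4.6.1 would count. This does not depend on how the note is read.

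The consequence does depend on it. A timed pre-infusion event is in neither TEAE column if the note applies to the first OLE infusion. It is an OLE TEAE if the note means Day 1 only. An untimed event is an OLE TEAE either way. Complete loss from the TEAE tables is therefore one possible outcome, limited to events with a recorded time, and it is not loss from reporting.

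The number affected is likely very small: part of one day, in participants who entered the OLE. It cannot be computed from the documents.

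**What to change.** Amend SAP Table 5 and its note:

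1. For participants entering the OLE, an RCP TEAE has onset from the first RCP dose up to immediately before the start of the first OLE infusion. An OLE TEAE has onset at or after that start.
2. In the note, the infusion used for comparison is the first infusion of the respective period. A switch-day event timed before the first OLE infusion is assigned to the RCP.
3. Switch-day events with no recorded time follow one stated default. Keeping them in the OLE by date preserves their present assignment. Assigning them to the RCP would also be workable, provided the choice is made before unblinding.

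This also brings Table 5 into line with SAP 1.2 and removes the gap relative to Protocol 9.4.6.1. The cost is a few lines of SAP text and one condition in the AE derivation. No new data are needed.
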